2 STUDY OBJECTIVES

2.1 Primary Objective

This study will determine whether T-cell depletion followed by belatacept and daily maintenance therapy with sirolimus will permit recipients of renal allografts to avoid rejection and eventually be weaned to belatacept monotherapy maintenance immunosuppression. The primary endpoint will be the number of patients successfully withdrawn from sirolimus for 1 year after their last dose of sirolimus. “Successfully withdrawn” will be defined as a patient off sirolimus without clinical or biopsy evidence of rejection.

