4.2 Analyses

Demographics and Baseline Characteristics

Demographic and baseline characteristics of patients will be summarized descriptively by treatment group, by means and standard deviations (SDs) for continuous variables and frequency distribution for categorical variables. Summaries will be performed based on the data set.

Efficacy Analyses

No formal statistical hypothesis testing will be performed for the primary endpoint. All efficacy analyses will generally be descriptive in nature. The primary efficacy analysis will be to assess the proportion of patients successfully withdrawn from sirolimus for one year. The point estimate of this proportion and the exact two-sided 95% confidence interval (CI) will be provided for each treatment group. A patient will be considered to be successfully withdrawn from immunosuppression for one year if the patient has been administered only belatacept for a period of 365 days, following successful completion of sirolimus, and has not experienced biopsy-proven acute rejection, formation of DSA, or graft loss for this same period of 365 days. Secondary efficacy outcome measures involving incidences and proportions will be descriptively summarized with point estimates and exact, two-sided 95% CIs by treatment group. Other secondary efficacy outcome measures will be descriptively summarized by means and SDs for continuous outcomes and frequency distributions for categorical outcomes.

Safety Analyses

All AEs and SAEs will be summarized by treatment group. Laboratory values will also be descriptively summarized.

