6.6 Treatment of Rejection

Biopsy proven acute rejection episodes will be treated based on the discretion of the transplant physician or surgeon. It will be permissible but not mandatory to continue protocol participation for patients who experience an early steroid sensitive rejection as described above. Presumed rejection episodes will be confirmed by biopsy as soon as possible after the initiation of symptoms. Biopsies will be performed at the Emory Transplant Clinic if at all possible. If patients are greater than a 24-hour trip from the center, the PI may elect to have the biopsy performed by a qualified transplant physician or surgeon. The Banff grade of rejection will be documented in the clinical case file and the date of the first episode of acute rejection will be the date the rejection is confirmed by biopsy. Management of rejections must be based on biopsy and clinical findings.

Patients with suspected rejection will undergo physical exam, laboratory evaluation, ultrasound examination of the kidney, and percutaneous renal biopsy accompanied by blood collection for peripheral phenotype analysis, transcriptional analysis and evaluation of donor specific alloreactivity. Biopsies will be evaluated by the attending transplant physician and reviewed with a pathologist skilled in the evaluation of renal transplant biopsy material. Biopsies will be evaluated using the Banff criteria for determination of allograft rejection.¹³⁰⁻¹³² Patients with biopsy proven rejection will be treated with methylprednisolone 500mg x 1-3 days. Failure to respond to methylprednisolone in no more than 3 days, or rapid worsening of graft function despite methylprednisolone therapy will prompt use of an approved antilymphocyte agent or other therapies deemed appropriate by the attending transplant physician or surgeon. After treatment of a steroid resistant rejection episode, patients will be discontinued from study treatment/immunosuppressive weaning and returned to a maintenance regimen established at the discretion of the attending transplant physician or surgeon in keeping with standard of care immunosuppression for renal transplantation. After treatment of a steroid sensitive rejection episode, patients may be restarted on the previous level of immunosuppression. The dosing and intensity of the regimen for maintenance

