7.9 Renal Biopsy

Renal biopsy is a standard procedure that carries a low risk for the patient of bleeding. The risk is minimized by guidance with real time ultrasound and decreases with time from the transplant procedure. Biopsies performed within one week of transplant carry a 1-2% risk of significant bleeding (defined as requiring some intervention, either transfusion or surgery). This decreases to less than 0.5% after the 4th week as the kidney scars into place. Transplanted kidneys are easier to biopsy than native kidneys due to their location in the iliac fossa as opposed to in the flank. Biopsy will not be performed on patients with a platelet count <80 unless clinically indicated. A biopsy shall be considered clinically indicated when obtained to evaluate any abnormality and required by the attending physician to guide clinical care.

During a biopsy, a patient will feel mild burning for several seconds during instillation of a local anesthetic agent. Thereafter, the patient will feel a pushing sensation, but usually little pain, as the needle enters the kidney. There may be some mild residual pain. In the event that significant bleeding is suspected, either through clinical observation or a significant decrease in hemoglobin, an ultrasound will be performed. Transfusion will be administered as necessary or the patient will be taken to the operating room for direct control of the bleeding.

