| BK viremia/viruria PCR | | X | | | X |
| Adverse Events | X | X | | | X |
| QoL | | | | X | |
| Neurologic Exam | | | X | | |
| Immunogenicity | | | | X ^a | |

^a These are specific study related assays for reporting purposes.

Long-Term Follow-Up Cohort 1

| Tests / Evaluations | Every 6months | Yearly |
|----------------------------------------------------------------------|----------------------|----------------|
| Telephone Reporting | X | |
| Serum Chemistry/ lipids /CBC | X | |
| Sirolimus trough | | X |
| Lymphocyte subsets | X | |
| Peripheral transcription | | X |
| CMV and EBV PCR | X | |
| BK viremia/viruria PCR | X | |
| PRA | | X |
| Anti-Donor Antibody | | X |
| Donor-specific and third party mixed lymphocyte responsiveness/ ICCS | | X |
| Renal Biopsy | | X ^b |
| Intragraft mRNA Analysis | | X ^b |
| Adverse Events | X | X |
| QoL | X | |
| Neurologic Exam | X | |
| PK | | |
| Immunogenicity | X | |

=

^b To be performed prior to weaning patient to monotherapy (generally at 12 months) and again after stable on monotherapy as clinically indicated.

Long-Term Follow-Up Cohort 2

| Tests / Evaluations | Monthly after Year 1 | Every 3 months from 6 - 24Months | Every 6 months | Yearly |
|----------------------------------------------------------------------|-----------------------------|-----------------------------------------|-----------------------|----------------|
| Telephone Reporting | | | X | |
| Serum Chemistry/ lipids /CBC | X ^c | | X | |
| Sirolimus trough ^d | X | | | X |
| Lymphocyte subsets Ki67 | | | X | |
| Peripheral transcription | | | | X |
| CMV and EBV PCR | | X | X | |
| BK viremia/viruria PCR | | X | X | |
| PRA | | | | X |
| Anti-Donor Antibody | | | | X |
| Donor-specific and third party mixed lymphocyte responsiveness/ ICCS | | | | X |
| Renal Biopsy | | | | X ^b |
| Intra-graft mRNA Analysis | | | | X ^b |
| Adverse Events | X ^e | | | |
| QoL | | | X | |
| Neurologic Exam | | | X | |
| Immunogenicity | | | X | |

^cStudy participants may have these labs drawn more or less frequently as deemed clinical necessary by the investigator.

^dStudy participants who are not weaning sirolimus and are on a stable, low dose can have trough levels monitored as frequently as a monthly basis or as clinically indicated.

^eIf study participant is on a stable dose of sirolimus, not weaning, and receiving commercial belatacept as an outpatient, then adverse events may be assessed every three months.

Year 1 Medication Flowchart

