9.2 Post-transplant Monitoring

Post-transplant Blood Monitoring. In general, functional monitoring will proceed in keeping with the standard of care for kidney transplantation at the Emory Transplant Center. Blood for testing of renal function (creatinine, BUN, hemoglobin/hematocrit) and electrolytes (including sodium, potassium, chloride, bicarbonate, magnesium, calcium and phosphorous) will be drawn daily until discharge and at least two times weekly for one month. Patients will be monitored weekly for at least 3 months or until the ALC exceeds 500 cells/mm³, whichever is longer. Thereafter, renal function will be assessed at least every two weeks until they reach their one-year evaluation. Lymphocyte repopulation and specific Ki67 and T_{REG} and B_{TRANS} phenotypes will be assessed monthly until 1 year after sirolimus elimination, and then every 3 months through 5 years by analysis of 7ml of heparinized blood by flow cytometry.

Biopsy Monitoring. A protocol biopsy will be performed following allograft reperfusion. Additional protocol biopsies will be performed at 6 months, and when the criteria for weaning to monotherapy belatacept are met (generally this will be during the second post transplant year) and again when the patient has been weaned to monotherapy belatacept for three months. An additional biopsy will be performed one year after weaning off sirolimus. It is assumed that histological acute allograft rejection is indicative of under-immunosuppression. Since histological rejection has been documented to occur in the absence of clinical renal dysfunction (so-called sub-clinical rejection) in up to 30% of persons with stable allograft function, it is reasonable to assume that some patients studied in this trial will have sub-clinical rejection, and thus be inappropriate for further immunosuppressive reduction. Protocol biopsies are thus clinically indicated to pre-empt inappropriate immunosuppressive weaning, as well as to detect other occult pathology

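### The schedule leaves biopsy on stable belatacept monotherapy optional while 9.2 orders it at three months and one year, and 4.2 counts an unbiopsied patient as a success

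*Combined protocol and SAP*

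**What the plan says.** Both long-term follow-up tables in 8.1 list renal biopsy in the yearly column with superscript b. The footnote, printed under the Cohort 1 table, reads: "To be performed prior to weaning patient to monotherapy (generally at 12 months) and again after stable on monotherapy as clinically indicated". Neither table shows a biopsy timed from the end of sirolimus. Section 9.3, on evaluations during the treatment period, refers the reader to the Section 8 flowcharts for tests and their timing.

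Section 9.2 (Biopsy Monitoring) orders a protocol biopsy when the weaning criteria are met and "again when the patient has been weaned to monotherapy belatacept for three months". It then adds: "An additional biopsy will be performed one year after weaning off sirolimus". No exception for stable patients and no visit window is given. The section explains that histological rejection can be present without renal dysfunction, and concludes: "Protocol biopsies are thus clinically indicated to pre-empt inappropriate immunosuppressive weaning". It also gives detection of other occult pathology as a reason.

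Under 4.2 a patient is a success after 365 days on belatacept alone if the patient "has not experienced biopsy-proven acute rejection, formation of DSA, or graft loss for this same period of 365 days". Section 2.1 describes success as "a patient off sirolimus without clinical or biopsy evidence of rejection", for an endpoint set at one year after the last sirolimus dose. Neither section makes a completed biopsy a condition of success.

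**The concern.** The primary result is a descriptive proportion, so its meaning depends on how failure is looked for. Two instructions on the main histological check disagree, and the success rule does not notice whether the check was made. A centre following the footnote would biopsy only weaned patients who gave cause. A patient with silent rejection would then pass through the year and be counted as withdrawn successfully.

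Other checks remain: 9.2 calls for biopsy on a sustained creatinine rise of 30% or more or on clinical suspicion, and anti-donor antibody is tested yearly. These do not replace a planned biopsy for the condition that 9.2 describes, which is rejection while function is stable.

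The one-year biopsy, the last planned look, is due just as the 365-day period closes. If it slips by some days, 4.2 does not say whether what it shows belongs to the endpoint.

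**Working it through.** **1. The instructions side by side**

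| Point | 9.2 | 8.1, footnote b | 4.2 |
|---|---|---|---|
| Before weaning | Biopsy | Biopsy | – |
| 3 months on monotherapy | Biopsy | Only as clinically indicated | Not required for success |
| 1 year after sirolimus | Biopsy, no visit window | Only as clinically indicated | Not required for success; counted period is 365 days |

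**2. Does the yearly column settle it?** No. The 9.2 biopsies run from the last sirolimus dose, and the start of weaning varies: the Year 1 Medication Flowchart places it in weeks 53-104. I count yearly visits from transplant.
- Earliest start, week 53 (month 12.2), taper of 2 to 6 months: last dose at months 14.2-18.2. The biopsies fall at months 17.2-21.2 (+3) and 26.2-30.2 (+12), away from the month 24 and 36 visits.
- Start at month 18, taper of 6 months: last dose at month 24. The biopsies fall at months 27 and 36, and the second coincides with a yearly visit.

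Coincidence depends on the patient, so the column neither supplies nor rules out the 9.2 biopsies.

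**3. Direction.** A biopsy that is not done cannot yield a biopsy-proven rejection. Under 4.2, missing histology can therefore leave the success count unchanged or raise it, never lower it.

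**4. The plan's own figures.** From 3.1 and 3.4: 20 enrolled, up to 20% (4) lost to rejection before withdrawal, 4 more ineligible or refusing, 50% success.
- Attempted: 20 − 4 − 4 = 12.
- Expected successes: 12 × 0.50 = 6.

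Both agree with 3.4.

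**5. Size per patient.** One patient reclassified moves the proportion by 1/12 = 8.3 points among those attempted, or 1/20 = 5.0 points among all 20 transplanted.

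The number reclassified, k, is not in the documents. As an assumption I show k = 0 to 3 of the 6 expected successes, with the exact (Clopper-Pearson) 95% intervals that 4.2 calls for:

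| k | Of 12 attempted | Of 20 transplanted |
|---|---|---|
| 0 | 50.0% (21.1-78.9) | 30.0% (11.9-54.3) |
| 1 | 41.7% (15.2-72.3) | 25.0% (8.7-49.1) |
| 2 | 33.3% (9.9-65.1) | 20.0% (5.7-43.7) |
| 3 | 25.0% (5.5-57.2) | 15.0% (3.2-37.9) |

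**The case against.** The best defence is that 9.2 is the detailed procedure, says these biopsies will be done, and itself calls protocol biopsies clinically indicated. On that reading the footnote only repeats 9.2. Biopsies tied to the weaning date would also not be expected as fixed columns in a table counted from transplant. Both points have weight: the text is contradictory and is not a settled waiver. They do not remove the conflict, because the first reason 9.2 gives, preventing inappropriate weaning, no longer applies once sirolimus has stopped, and 9.3 sends staff to the flowcharts for timing.

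The defence can also say that weaned patients have already had a biopsy free of rejection (6.2), that nothing is tested, and that the number misclassified is unknown. All of this stands and limits the size of the point.

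Three stronger readings are tempting, and the documents do not support them.

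- *Section 7.9 defines the footnote's wording.* It says: "A biopsy shall be considered clinically indicated when obtained to evaluate any abnormality and required by the attending physician to guide clinical care". That sentence explains an exception to the platelet-count limit and does not refer to the schedule.
- *Section 2.1 has no date limit and so conflicts with 4.2 on timing.* The sentence before its definition fixes the endpoint at one year after the last sirolimus dose, and 3.3 says the same.
- *Section 4.2 definitely excludes a rejection confirmed after day 365.* It contains no dating rule. Section 6.6 says that "the date of the first episode of acute rejection will be the date the rejection is confirmed by biopsy", and Appendix A uses the date on which added immunosuppression starts, but both are written for clinically suspected rejection. A silent finding on a scheduled biopsy just after day 365 is therefore unassigned, and a biopsy done by day 365 raises no difficulty.

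**Conclusion.** The point holds as a contradiction in how the primary endpoint is ascertained, and it should be repaired. Footnote b and 9.2 disagree on biopsy during stable monotherapy, 4.2 accepts a never-biopsied patient as a success, and the status of a slightly late one-year biopsy is open. Any resulting bias is upward, at 8.3 points per patient on 12 attempts or 5.0 on 20 transplanted.

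The total is unknown. It is zero if every 9.2 biopsy is done and confirmed by day 365, and the documents do not show which text was followed. The range of 0 to 3 patients is an illustration. A reader might apply the figure in 9.2 of up to 30% subclinical rejection to the 6 expected successes. That figure is an upper bound for stable grafts in general, not a rate for this regimen after a clear pre-weaning biopsy, so it does not support an estimate here. The intervals overlap widely and there is no hypothesis test; what is affected is the reported proportion and what it can be said to mean.

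**What to change.** - **8.1, footnote b:** match 9.2, with biopsy before weaning and at 3 and 12 months after the last sirolimus dose, for every patient not yet past those points. The documents do not show where Cohort 1 patients now stand, so apply it there only where it still can be.
- **4.2:** state that acute rejection on the one-year protocol biopsy is a failure even if the biopsy falls shortly after day 365, and say how late a biopsy may be and still count.
- **Reporting:** give the number of successes with a completed one-year biopsy. Beside the primary proportion, add one line counting successes without it as not successful, labelled as a lower bound.

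The cost is one footnote, a short addition to 4.2, one count and one table line. No biopsy is added beyond 9.2. If practice has followed the footnote, 12 weaned patients could have up to 12 × 2 = 24 further biopsies. At the 7.9 figure of under 0.5% significant bleeding each after the fourth week, that is fewer than 24 × 0.005 = 0.12 expected bleeds. The reported proportion may be slightly lower. The lower-bound line counts a refused biopsy as a failure, so it should accompany the main figure and not replace it.

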9.1 Pre-transplant Tissue Acquisition

Patients will be enrolled prior to transplantation to facilitate informed consent and baseline sample procurement. All patients will be specifically informed that protocol participation will not influence their receipt of the kidney being offered. Upon enrollment, patients will have standard hematology, chemistry, virology, and coagulation samples drawn. In addition, samples will be drawn for baseline serum (from 10 ml whole blood) and lymphocyte harvest (from 100ml whole heparinized blood). Serum and cells will be separated and used for baseline assays with excess cells cryopreserved. A separate 5 ml heparinized sample will be drawn for T cell subset phenotyping. The total amount of blood drawn for research purposes will not exceed 450ml in any six-week period.

At the time of transplantation, donor samples will be obtained from 120 ml heparinized whole blood from live donors, and a similar amount of blood or spleen or lymph node from deceased donors. Lymphocytes will be procured and cryopreserved by the Emory Transplant Center Biorepository (see Resources). Lymphocytes will only be used for studies related to this protocol. After the transplant, cryopreserved serum and cell samples will be utilized by the Sponsor-investigator for mechanistic analysis, storage, or distribution to collaborating laboratories. Samples may also be sent to collaborating sites for study-related mechanistic analysis.

9.2 Post-transplant Monitoring

Post-transplant Blood Monitoring. In general, functional monitoring will proceed in keeping with the standard of care for kidney transplantation at the Emory Transplant Center. Blood for testing of renal function (creatinine, BUN, hemoglobin/hematocrit) and electrolytes (including sodium, potassium, chloride, bicarbonate, magnesium, calcium and phosphorous) will be drawn daily until discharge and at least two times weekly for one month. Patients will be monitored weekly for at least 3 months or until the ALC exceeds 500 cells/mm³, whichever is longer. Thereafter, renal function will be assessed at least every two weeks until they reach their one-year evaluation. Lymphocyte repopulation and specific Ki67 and T_{REG} and B_{TRANS} phenotypes will be assessed monthly until 1 year after sirolimus elimination, and then every 3 months through 5 years by analysis of 7ml of heparinized blood by flow cytometry.

Biopsy Monitoring. A protocol biopsy will be performed following allograft reperfusion. Additional protocol biopsies will be performed at 6 months, and when the criteria for weaning to monotherapy belatacept are met (generally this will be during the second post transplant year) and again when the patient has been weaned to monotherapy belatacept for three months. An additional biopsy will be performed one year after weaning off sirolimus. It is assumed that histological acute allograft rejection is indicative of under-immunosuppression. Since histological rejection has been documented to occur in the absence of clinical renal dysfunction (so-called sub-clinical rejection) in up to 30% of persons with stable allograft function, it is reasonable to assume that some patients studied in this trial will have sub-clinical rejection, and thus be inappropriate for further immunosuppressive reduction. Protocol biopsies are thus clinically indicated to pre-empt inappropriate immunosuppressive weaning, as well as to detect other occult pathology

known to arise in transplanted kidneys that could confound the interpretation of the study.¹³³⁻¹³⁴ In the event that subclinical rejection is detected, the patient will receive anti-rejection therapy in keeping with the standard of care, generally an oral steroid taper over 30 days and reevaluation of the patient's need for chronic immunosuppression. A follow-up biopsy will be performed in 3 months to assess resolution of subclinical rejection. Subclinical rejection, once resolved, will not in and of itself remove the patient from consideration of weaning, if it occurs during a period of homeostatic repopulation.

Renal biopsies also will be performed if any sustained rise in serum creatinine of greater than or equal to 30% of the baseline creatinine is detected. Baseline creatinine will be defined as the mean of five stable serum creatinine values within the first three months post-transplant. Stable is defined as a variance of +/- 20% or less of any value. Clinical suspicion of allograft pathology based on other grounds (urine cytology, pyuria, proteinuria, etc.) also will be considered grounds for biopsy at the discretion of the attending physician. An attending transplant physician or surgeon will perform all biopsies. The risks of transplant kidney biopsy will be included in the informed consent process for the protocol. At the time of each biopsy (protocol or clinically indicated), blood will be drawn for peripheral phenotyping and lymphocyte harvest (50ml heparinized).

Patients will be evaluated for cellular alloreactivity, donor-specific hyporesponsiveness and viral specific responsiveness pre-operatively, at the time that sirolimus withdrawal commences, 3 months after sirolimus withdrawal, at the time of clinical rejections, and at study termination. This will require 50ml of heparinized blood to be drawn at these time points and cryopreserved for analysis.

